## Cover Letter

### Title:

## Efficacy of Vitamin D Supplementation in Females with Polycystic Ovary Syndrome: A Randomized Open-Label Delayed-Start Design

Clinical Trial Unit,

I am writing to submit my study, titled "Efficacy of Vitamin D Supplementation in Females with Polycystic Ovary Syndrome: A Randomized Open-Label Delayed-Start Design," for consideration in the Clinical Trial Unit. I am excited to present this research project for potential inclusion in your esteemed program.

Polycystic Ovary Syndrome (PCOS) is a prevalent and complex endocrine disorder that affects many women worldwide. The condition is characterized by a range of symptoms, including irregular menstrual cycles, hyperandrogenism, and polycystic ovarian morphology. There is a growing body of evidence suggesting a link between vitamin D deficiency and PCOS, as vitamin D plays a crucial role in various aspects of reproductive health and endocrine regulation.

Our study aims to investigate the efficacy of vitamin D supplementation as a potential therapeutic intervention for females with PCOS. The randomized open-label delayed-start design allows for a comprehensive examination of the long-term effects of vitamin D supplementation on PCOS symptoms and associated comorbidities. By comparing the outcomes between immediate and delayed-start groups, we hope to gain insights into the optimal timing of vitamin D intervention and its impact on the progression of PCOS.

[figure not shown]
The significance of this study lies not only in its potential to improve the quality of life for individuals with PCOS but also in its contribution to the broader field of reproductive medicine. If our findings support the efficacy of vitamin D supplementation, it could lead to the development of cost-effective and accessible treatments for a condition that affects millions of women worldwide.

I believe that the Clinical Trial Unit is the ideal platform for conducting this research due to its commitment to advancing clinical science and improving patient care. Our study adheres to rigorous ethical and methodological standards, and we are confident that it aligns with the objectives and values of your organization.

I kindly request that you consider our study for inclusion in the Clinical Trial Unit and appreciate the opportunity to discuss this research further. The date of ERC approval is 7th December, 2021

Thank you for your time and consideration.

Best Regards,

## Methodology

**Study Design:** This will be a randomized open label, delayed-start design trial conducted at Aga Khan University at Departments of: Biological & Biomedical Sciences, Pathology and Laboratory Medicine, Medicine (Endocrinology) and Family Medicine for a period of 2 years following approval from Clinical Trials Unit and Ethical Review Committee of Aga Khan University

**Sample Size calculation;** The sample size was calculated by PASS 11 software. In an equivalence test of means using two one-sided tests on data from two-periods, the minimum sample size that we will require is 142, 71 in each group with an inflation of 20% for loss to follow-up to achieve 80% power at a 5% significance level when the true difference between the means is 0.4, the standard deviation of the paired differences is 2.60.

**Eligibility Criteria:** Patients recently diagnosed with PCOS with presence of at least 2 of these 3 elements: clinical or biochemical signs of hyperandrogenism, chronic anovulation and polycystic ovaries (1) (from reports of available routine TVS), with VDD serum levels VD <20 ng/ml(10), age range 18- 45 years, from all ethnic background will be included. We will exclude patients who will be pregnant, with Hypercalcemia (plasma calcium concentrations > 2.65 mmol/L), Tuberculosis or other granulomatous disorders, Chronic liver disease or alanine transaminase (ALT) level 3 times higher than the normal limit, chronic, Kidney disease or serum creatinine >2.0 mg/dL, on drug Therapies i.e participants who had received VD injection in the last 3 months prior to recruitment in the study, oral contraceptives, hormonal replacement therapy, glucocorticoids, calcium supplementation, insulin-sensitizing drugs (incretin mimetic drugs, thiazolidinedione, sulfonylurea), lipid-lowering drugs or other drugs affecting insulin sensitivity or serum androgens (e.g., niacin, corticosteroids, beta-blockers, calcium channel blockers, thiazide diuretics), anti-epileptics, anti-retroviral, cholestyramine, anti-fungal, statins, H2 blockers, immunosuppressant, chemotherapeutic agents, antimicrobials (Rifampicin, Isoniazid, Hydroxychloroquine) or any other drug modifying lipid metabolism in the previous 3 months prior to study , patients suffering from congenital adrenal hyperplasia, Cushing's syndrome, androgen-secreting tumors, type 2 Diabetes Mellitus, renal, hepatic or thyroid disorders, hyperparathyroidism, malabsorption syndromes, Chronic Kidney Disease, Hepatic failure, cystic fibrosis, vaginal bleeding of unknown etiology or /and suffering from COVID-19 (within 3 months).

**Recruitment of Subjects:** All diagnosed PCOS subjects as per the Rotterdam criteria visiting Endocrine, Family Medicine and/or Gynae Obs clinic qualifying the inclusion criteria with VD levels <20 ng/ml (7, 9, 10) and age range 18 to 45 years will be invited to participate in the study after acquiring written informed consent.

**Randomization:** Subjects will be brought to Clinical Trial Unit (CTU) of AKU which has full-fledged clinical space for consultation, trial and laboratory support. Randomization will be

done using the permuted block randomization technique generating blocks with equal representation of all arms in a 1:1 ratio. The randomization list will be generated using the AKUH developed randomization software (<http://www.randomizer>). The randomization list is confidential and will be kept within the premises of CTU under restricted access. Subjects will be randomized into Group A (Intervention) and B (Control) and will receive the treatment protocol

**Intervention Group (Table 2) for the initial 12 weeks will receive:** VD supplementation (600,000 IU I/M) once during the study period and elemental calcium 1000 mg/day . However from 12-24 weeks they will receive standard PCOS treatment, lucophage XR 750 mg once at dinner for 15 days then twice daily, capsule Progeffik 100 mg once at night every 3 weeks, then 1 week off and calcium 1000 mg/day.

**Control Group for the initial-- 12 weeks** the control group will receive the standard treatment for PCOS , Glucophage XR 750 mg once at dinner for 15 days then twice daily and Capsule Progeffik 100 mg once at night every 3 weeks, then 1 week off

However, from 12- 24 weeks they will receive VD supplementation (600,000 IUI/M) once during the study period , calcium 1000 mg/day and standard PCOS treatment will be continued

	Group A (intervention)	Group B (Control)
Initial 12 weeks	Vitamin D: 1. VD supplementation (600,000 IU I/M once ) 2. Calcium 1000 mg/day	Standard PCOS; 1. Glucophage XR 750 mg once at dinner for 15 days then twice daily 2. Capsule Progeffik 100 mg once at night every 3 weeks, then 1 week off
At 12 weeks after consultation and biochemical tests treatment protocol will be changed as mentioned 
 
• Vitamin D & Calcium will be given to Group B with continuation of standard PCOS treatment (point of care)
 
• Standard PCOS care for Group A with continuation of calcium (point of care)
 
		
After 12 weeks	Standard PCOS; 1. Glucophage XR 750 mg once at dinner for 15 days then twice daily 2. Capsule Progeffik 100 mg once at night every 3 weeks, then 1 week off 3. Calcium 1000 mg/day (contd.)	Vitamin D: 1. VD supplementation (600,000 IU I/M) 2. Calcium 1000 mg/day 3. Standard PCOS Contd

**Data Collection:** Randomization and drug dispensing will be followed by detailed history, physical examination, biophysical and biochemical parameters estimation by research team. The data will be collected on the following variables ; Body Mass index., Waist circumference (WC)Waist -Hip Ratio, Biochemical estimation ( results of following routine tests are available (Human Sex Hormone-Binding Globulin (SHBG), Total Testosterone (TT), Human Insulin and Glucose) to be included in the profile. For

[figure not shown]
estimation of Total Antioxidant Capacity (TAC), serum calcium and phosphorous levels, phlebotomist will collect blood samples (3 cc) by vein puncture).

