**Calculations;**

- i. HOMA-IR : HOMA- IR index, a commonly used marker of IR, will be calculated using the formula:  $\text{HOMA-IR} = \frac{\text{fasting glucose levels [mmol/L]} \times \text{fasting insulin levels } [\mu\text{U/mL}]}{22.5}$  (34).
- ii. Free Androgen Index will be derived from TT and SHBG, normally measured in nanomoles per liter.  $\text{FAI} = 100 (\text{TT} / \text{SHBG})$

**Outcome : Follow- up visits at 12 weeks (Study Mid Pont):** At 12 weeks follow up, compliance to supplementation and occurrence of any adverse effect will be assessed by research team allocated members in the respective clinics. Moreover, drug for 12 weeks (as per group allocation) will be dispensed and any other queries of participants will be responded. Fasting blood sample (10 ml) will be collected for estimation of SHBG, TT, Human Insulin, Glucose, serum calcium and phosphorous and TAC in both groups and VD and serum albumin estimation in Group A. At this point of time, **treatment protocol of both groups will be changed** (Table 2).

1. **Follow- up visits at 24 weeks (study End Point):** After completion of 24 weeks study exposure, subjects will be informed about completion of study. Blood samples in fasting state will be collected for repeat analysis in Multi Disciplinary Lab (MDL) for all the biochemical parameters (FAI, HOMA IR and TAC) and VD and serum albumin estimation in Group B. Figure 6: Complete cycle of each patient in control and intervention group for a period of 24 weeks

**Biohazardous Samples:** According to the WHO the serum samples have low viral concentration. However, the centrifugation is a risk for aerosol generation and COVID exposure. To minimize the risk, we will ; Train the research staff about the Basics of Biosafety, Biosecurity & Bio risk Management approach for collection & processing of samples. All samples will be treated as potentially infectious, use of proper PPE will be mandatory while handling samples. After centrifugation, staff will wait for 10 minutes before opening the centrifuge. In case of Breakage the already defined laboratory protocols (available in safety manual) will be followed. For liquid waste disposal, will use 5% Hypochlorite.

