Investigator and study coordinator will follow up any adverse events and serious adverse events.

**Plan of analysis:** Data will be analyzed using STATA version 15. The main analysis for each outcome will be performed at the subject level using the **intention-to-treat (ITT) principle**, meaning that all participants with a recorded outcome will be included in the analysis and will be analyzed according to the treatment group to which they were randomized. Results will be presented as mean and standard error/ median (IQR) for the outcomes. Pretreatment, 12 weeks and 24 weeks post treatment levels of the outcomes will be assessed by repeated measure ANOVA/ Friedman test as appropriate. Categorical variables will be reported as frequency and percentages and will be assessed by chi-square/ fisher exact test. Unadjusted and adjusted beta coefficient with 95% CI will be reported by using Generalized estimating equation (GEE) to determine the association of various independent factors with the outcomes. We will adjust for the independent variables and determine the association of factors causing a greater decline in outcomes by multivariable GEE. Plausible interactions and confounders will also be assessed. A p value of  $< 0.05$  will be considered as significant throughout the study

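### The 142 patients and 80% power come from a two-period equivalence calculation, but the protocol has an efficacy aim and plans only difference tests, so the stated power does not apply to its analysis

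*Protocol*

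**What the plan says.** The sample size paragraph in the Methodology bases the trial's size on a calculation described as "In an equivalence test of means using two one-sided tests on data from two-periods". The inputs are 80% power, a 5% significance level, a 20% inflation for loss to follow-up, and that the "true difference between the means is 0.4, the standard deviation of the paired differences is 2.60". The result is 142 patients, 71 per group. The paragraph gives no equivalence margin and does not say which outcome the 0.4 and 2.60 describe.

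The rest of the protocol reads differently:

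- **Aim (Cover Letter):** "Our study aims to investigate the efficacy of vitamin D supplementation as a potential therapeutic intervention for females with PCOS", and "By comparing the outcomes between immediate and delayed-start groups, we hope to gain insights into the optimal timing of vitamin D intervention".
- **Treatments (group descriptions and table under Randomization):** patients are randomised 1:1. Group A goes from vitamin D plus calcium to standard care plus calcium. Group B starts on standard care; from week 12 it receives vitamin D, and "calcium 1000 mg/day and standard PCOS treatment will be continued".
- **Outcomes (24-week follow-up):** "all the biochemical parameters (FAI, HOMA IR and TAC", three quantities on different scales.
- **Plan of analysis:** outcome levels before treatment and at 12 and 24 weeks "will be assessed by repeated measure ANOVA/ Friedman test as appropriate". "Unadjusted and adjusted beta coefficient with 95% CI will be reported by using Generalized estimating equation (GEE". Significance is p < 0.05 throughout. There is no equivalence hypothesis, margin or pair of one-sided tests.

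**The concern.** A power figure holds only for the test it was computed for. Two one-sided tests ask whether the difference lies inside a margin. In that setting 0.4 is a true difference small enough for equivalence still to be declared. The planned ANOVA and GEE ask whether the difference is other than zero, and for that question neither 0.4 nor 80% has been justified.

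The two-period paired formula does not match the design either. It compares the same two treatments within each patient, whereas here the second-period treatments are not the first-period treatments exchanged between groups.

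A reader of an efficacy trial will naturally take 80% power with 0.4 as the detectable effect. A non-significant result could then be read as good evidence that vitamin D does not work. The protocol gives no basis for that reading.

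**Working it through.** **Inputs from the sample size paragraph:** N = 142 (71 per group), d = 0.4, SD of paired differences = 2.60, power 80%, level 5% (taken as 5% for each one-sided test), inflation 20%. The margin is not given.

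**Step 1. Can 142 be reproduced?** Not from the stated inputs alone. For a two-period equivalence test, SE = 2.60/√N and, approximately, margin = d + (1.645 + 0.842) × SE. The margin each N would imply for 80% power (exact t-based calculation) is:

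| N in the formula | Implied margin |
|---|---|
| 142 | 0.945 |
| 118 | 0.999 |
| 71 | 1.175 |
| 59 | 1.253 |

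Example with N = 118: SE = 2.60/√118 = 0.239, and 0.4 + 2.487 × 0.239 = 0.995 (0.999 exactly). With an assumed margin of ±1.0, 118 patients give 80.2% power, and 118 × 1.2 = 141.6, which rounds up to 142. So 142 may well be a genuine equivalence calculation with an unreported margin of 1.0, but that is an inference.

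**Step 2. Evaluable patients per group (assumed from the 20%).** 71 × 0.8 = 56.8, or 71/1.2 = 59.2. I use 57 and 59, with 71 as the no-loss case.

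**Step 3. If 0.4 were the effect to detect.** Two-sample t test, two-sided 5%, SE = SD × √(2/n), noncentral t. The between-group SD is not given, so two values are assumed: 2.60, and 2.60/√2 = 1.84.

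| Assumed SD | n = 57 | n = 59 | n = 71 | n per group for 80% |
|---|---|---|---|---|
| 2.60 | 13% | 13% | 15% | 665 |
| 1.84 | 21% | 22% | 25% | 333 |

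These two values are a reasonable bracket. If 2.60 is the SD of change from baseline, an unadjusted analysis of change uses 2.60. A baseline-adjusted analysis has residual SD 2.60 × √((1 + ρ)/2), taking equal SDs at both visits and correlation ρ between them. That runs from 1.84 at ρ = 0 to 2.60 at ρ = 1.

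**Step 4. The reading kindest to the plan.** Treat the test as a paired, two-period test of a difference of 0.4 with SD 2.60. Power is 38% with 118 patients and 44% with all 142 (45% by the normal approximation).

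**Step 5. What 71 per group does deliver.** The between-group difference detectable with 80% power is approximately (1.960 + 0.842) × √(2/n) SD. For n = 57 this is 2.802 × 0.187 = 0.525; the exact value is 0.529.

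| n per group | In SD units | Units if SD 2.60 | Units if SD 1.84 |
|---|---|---|---|
| 57 | 0.529 | 1.38 | 0.97 |
| 59 | 0.520 | 1.35 | 0.96 |
| 71 | 0.473 | 1.23 | 0.87 |

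**Step 6. If equivalence really is the aim.** A between-group test with a true difference of 0.4 reaches 80% power only at these margins: 1.63, 1.61 and 1.50 for n = 57, 59 and 71 with SD 2.60, or 1.26, 1.25 and 1.17 with SD 1.84. All exceed the 1.0 that would reproduce 142 in Step 1.

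**The case against.** Several counter-arguments deserve weight.

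- **No arithmetic error is shown.** True: with a margin of 1.0 the sum works. The fault is a mismatch between the calculation and the planned analysis, not a slip in the calculation.
- **The low power figures assume a target the protocol never sets.** Also true. They show what follows if 0.4 is read as the detectable effect; they are not the trial's power, and the finding does not rest on them.
- **Repeated-measures ANOVA is most directly a within-patient analysis, so the paired reading is the fairer one.** It is reported in Step 4 and still falls well short of 80%.
- **The assumed SDs are not a full bound.** An unadjusted comparison at a single visit could have a larger SD: at a between-visit correlation of 0.7 it would be 2.60/√(2 × 0.3) = 3.36, and power for 0.4 would drop to 9–11%. That makes the position worse.
- **Every patient receives the same vitamin D dose before or after standard care (Strength & Limitations), which may explain the two-period framing.** It may, but the treatments still do not swap, and no equivalence test follows from it.
- **The aims are quoted from the Cover Letter, some front matter is absent from the public text, and an unseen SAP may hold the margin, contrast and time point.** A SAP could supply those details. It could not make an equivalence power figure apply to the difference tests that the protocol itself fixes.

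**Conclusion.** The concern holds. The only justification for the trial's size is a power statement for an equivalence test that matches neither the stated aim nor any planned analysis. This follows from the text alone and needs no numerical assumption.

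How far real power falls short cannot be determined without an outcome, a target effect and an SD. None of the readings tried gives 80% power to detect 0.4: they range from about 13% to 25% between groups (SD assumed 2.60 or 1.84) and from 38% to 45% paired. The one figure that does not depend on the outcome is that 57–59 evaluable per group has 80% power for about 0.52–0.53 SD of the analysed quantity, in a two-sided 5% two-group comparison.

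**What to change.** Rewrite the sample size paragraph for the comparison the trial intends to make:

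1. Remove the equivalence and two-period wording.
2. Name the outcome, time point and between-group contrast that the size refers to, and give the source of the SD.
3. State what 71 per group delivers, for example: with 57–59 evaluable per group, the between-group comparison has 80% power (two-sided 5%) for a difference of about 0.52–0.53 SD, where SD means the SD of change if unadjusted or the residual SD if baseline-adjusted.
4. Add a sentence on why a difference of that size matters for the named outcome. If 0.4 units must be detectable, say openly that 71 per group may not achieve it.

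If equivalence to standard care is the real aim, state the margin, put the matching between-group pair of one-sided tests in the Plan of analysis, and recompute the power using the margins in Step 6.

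The cost is one rewritten paragraph (plus one analysis statement on the equivalence route), handled as an amendment because the Cover Letter records ethics approval. The rewording itself needs no extra patients. Whether 71 per group is enough depends on the outcome and effect then named. The stated detectable difference will look less favourable, and the sponsor must commit to one outcome and contrast.

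### A 20% inflation, read literally as N × 1.2, covers only about 16.7% loss to follow-up; if 118 women are needed, 142 falls 4 to 5 short at 20% loss (minor)

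*Protocol*

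**What the plan says.** The Sample Size calculation paragraph of the Protocol's Methodology section is the only place where the number of women is derived. The method is given as "In an equivalence test of means using two one-sided tests on data from two-periods", and the result and the allowance together as "the minimum sample size that we will require is 142, 71 in each group with an inflation of 20% for loss to follow-up". The target is "to achieve 80% power at a 5% significance level". Two numerical inputs are given: "the true difference between the means is 0.4" and "the standard deviation of the paired differences is 2.60". The Randomization paragraph sets 1:1 allocation ("generating blocks with equal representation of all arms in a 1:1 ratio").

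The paragraph does not print the equivalence limits, the number required before inflation, the expected loss rate, or whether the allowance was made by multiplication or division.

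The Plan of analysis includes participants who have a recorded outcome, so a woman lost before measurement reduces the analysed sample. The Potential Risks paragraph names loss to follow-up and noncompliance as risks but gives no rate.

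**The concern.** To keep N evaluable women after a fraction L is lost, one must enrol N/(1 − L). For L = 20% that is N/0.8, an increase of 25%. Adding 20% is not enough, because the loss applies to the enlarged sample and not to N.

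The paragraph ties the 20% to loss to follow-up and presents 142 as the minimum that delivers 80% power. If the 20% is both the expected loss and the amount added, the evaluable sample is 4% below the number needed, whatever that number is. The effect on this trial is small. The same step would, however, carry over into any recalculation with other inputs, and the gap in women would grow in proportion to N.

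**Working it through.** **Inputs.** From the Sample Size calculation paragraph: two one-sided tests on two-period data, significance 5% (taken as 5% for each one-sided test), power 80%, assumed difference 0.4, SD of paired differences 2.60, total 142, 71 per group, 20% inflation. Not in the protocol and therefore assumed: equivalence limits ±Δ, with Δ = 1.0 as the base case and 0.95 to 1.05 as the range shown.

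**Step 1: the part that needs no limit.**
- Literal reading: enrolled = 1.2N.
- After 20% loss: 1.2N × 0.8 = 0.96N.
- Loss fully covered: 1.2(1 − L) = 1, so L = 1 − 1/1.2 = 16.7%.

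**Step 2: can 142 be reproduced?** Not from the printed inputs alone, because this test has no sample size without Δ. With SE = 2.60/√N, t on N − 2 degrees of freedom, and s the estimated SE, power is the average over s of

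max{0, Φ[(Δ − t·s − 0.4)/SE] − Φ[(−Δ + t·s − 0.4)/SE]}.

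| Assumed Δ | N for 80% power | N × 1.2, rounded up | N / 0.8, rounded up |
|---|---|---|---|
| 0.95 | 140 | 168 | 175 |
| 1.00 | 118 | 142 | 148 |
| 1.05 | 101 | 122 | 127 |

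At Δ = 1.0, power is 79.86% at N = 117 and 80.16% at N = 118, so 118 is the first N to reach 80%. The normal approximation agrees closely: [2.60 × (1.645 + 0.842)/(1.0 − 0.4)]² ≈ 116.1. Then 118 × 1.2 = 141.6, rounded to 142, and per group 59 × 1.2 = 70.8, rounded to 71. Both printed figures are matched from a round limit. (Reading 2.60 as a within-subject SD with Δ = 1.25 also gives 118.)

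**Step 3: could division have been used?** 113/0.8 = 141.25, which rounds up to 142. The limit that gives 80% power at N = 113 is about 1.012. The fit is poorer: 113 cannot be split 1:1, and per group 56/0.8 = 70 while 57/0.8 = 71.25, which rounds up to 72. If instead 142 were the number before inflation, the implied limit would be about 0.945.

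**Step 4: consequence if N = 118.**
- Women remaining at 20% loss: 142 × 0.8 = 113.6, which is 118 − 113.6 = 4.4 short.
- Loss that 142 covers: 142 − 118 = 24 women, and 24/142 = 16.9%.
- Power at Δ = 1.0: 78.6% at N = 113 and 78.9% at N = 114, against 80.2% at N = 118.
- Full cover of 20% loss: 118/0.8 = 147.5, so 148 (59/0.8 = 73.75, so 74 per group).

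**Step 5: does the size of the power loss depend on Δ?** Hardly. If 118 gives 80%, then by the normal approximation 113.6 gives Φ[(1.645 + 0.842) × √(113.6/118) − 1.645] ≈ Φ(0.795) ≈ 78.7%. No limit enters this calculation.

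**The case against.** The strongest reply is that the protocol states neither the operation nor the number before inflation, and that the limits of ±1.0 were chosen because they return 118. Using 118 to show that 142 is short is then partly circular. Required N is very sensitive to the limit: at 1.02, power with 113 women would be about 80.9%, and 142 would survive a 20% loss. Division also remains arithmetically possible. Further, inflating by 20% is not the same as predicting 20% loss. Read strictly, the paragraph adds 20% and does not say that 80% power holds after a fifth of the women are gone.

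Much of this stands. A reader might infer that the trial misses 80% power on its own stated inputs. The protocol does not support that, because neither N nor power can be computed from the printed inputs, and every specific figure (118, 16.9%, 78.6%) rests on an assumed limit. A reader might also infer that six more women must be enrolled. The effect is too small to require that.

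Two things remain. The ordinary meaning of a 20% inflation is multiplication by 1.2, and the 4% shortfall at 20% loss then follows for any N and any limit. And 20% is the only rate attached to loss to follow-up. If another rate was meant, the paragraph still needs to say so.

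**Conclusion.** The point holds as a minor, conditional correction. On the literal wording, the allowance fully covers about 16.7% loss and not 20%. This rests only on reading the inflation as multiplication and the 20% as the loss to be covered.

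If the limits are also assumed to be ±1.0, the required number is 118, 142 covers 16.9% loss, and at 20% loss the trial has 113 to 114 evaluable women with power of about 78.6% to 78.9%. That is roughly 1 to 1.5 percentage points below target, and no decision about the trial turns on it. Multiplication is the more plausible origin of 142 because it reproduces both printed figures from a round limit, but it is inferred and not stated. The missing limit is the more basic gap in the paragraph: without it, 142 cannot be checked from the protocol.

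**What to change.** In the Sample Size calculation paragraph, print the equivalence limits, the number of evaluable women required before inflation, and the expected loss rate.

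If these prove to be ±1.0, 118 and 20%, add a sentence to this effect: 118 evaluable women are required; enrolling 142 covers about 17% loss; at 20% loss about 113 to 114 women remain and power is about 79%; full cover would need 148 (74 per group). The figures 118, 17% and 79% should not be entered as facts until the sponsor has confirmed the limits and N from the original sample size output.

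In any recalculation, divide by (1 − expected loss) instead of multiplying by 1.20.

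The cost is one or two sentences and a slightly less favourable stated figure. No added patients are needed.

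### Pregnancy is an exclusion, but the week-12 visit has no pregnancy check before Group B's single 600,000 IU injection or Group A's start of Glucophage and Progeffik

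*Protocol*

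**What the plan says.** The Eligibility Criteria (Protocol, Methodology) admit women aged 18 to 45 and state: "We will exclude patients who will be pregnant, with Hypercalcemia (plasma calcium concentrations > 2.65 mmol/L". No other part of the available text mentions pregnancy.

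Treatment is set out under Intervention Group, Control Group and Table 2. Group A's first-period treatment is "VD supplementation (600,000 IU I/M) once during the study period and elemental calcium 1000 mg/day". Group B starts on standard PCOS drugs, and its injection follows later: "However, from 12- 24 weeks they will receive VD supplementation (600,000 IUI/M) once during the study period". In the second period Group A starts Glucophage XR and Progeffik and continues calcium.

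Table 2 places a step before the switch: "At 12 weeks after consultation and biochemical tests treatment protocol will be changed as mentioned". The week-12 visit is described under Outcome, where "compliance to supplementation and occurrence of any adverse effect will be assessed by research team allocated members in the respective clinics". A fasting blood sample is then taken in both groups for SHBG, total testosterone, insulin, glucose, calcium, phosphorus and total antioxidant capacity, with vitamin D and albumin added in Group A. The same paragraph then changes the treatment of both groups.

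The Sample Size paragraph says: "the minimum sample size that we will require is 142, 71 in each group with an inflation of 20% for loss to follow-up".

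**The concern.** An exclusion applied at recruitment protects a woman only from treatment that starts at about that time. In this design half of the participants receive the study injection a full treatment period later, and the other half start two new drugs at that same point. For every participant, then, new treatment begins at least 12 weeks after the pregnancy criterion was applied, and nothing in the visit schedule applies it again.

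What is at stake is participant safety and adherence to the trial's own criterion. Tablets can be stopped once a pregnancy is recognised; a single intramuscular dose cannot be taken back. A check made after the injection comes too late.

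**Working it through.** No figure in the plan needs to be reproduced, so the check sets the relevant provisions side by side.

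1. **When pregnancy is assessed.** The Eligibility Criteria are applied before a woman is invited and randomized. The future tense of the exclusion could be read as covering the whole study. If it applies at entry only, it is not re-applied at week 12. If it applies throughout, the protocol gives no means of applying it at week 12. Both readings leave the same gap.

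2. **When new treatment starts.** Group B's injection falls in weeks 12 to 24, so the interval from entry is at least 12 weeks. Group A's Glucophage and Progeffik start at week 12.

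3. **What stands between the two.** Table 2 requires a consultation and biochemical tests. The Outcome paragraph names the tests, and none detects pregnancy. It names compliance and adverse effects as the matters to assess. The consultation has no stated pregnancy content.

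4. **Comparison with another exclusion.** Hypercalcemia is in the same sentence as pregnancy in the Eligibility Criteria. Serum calcium is measured at week 12 in both groups. So one of the two conditions is looked at again before the switch and the other is not.

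5. **Whether a later safeguard helps.** Under Drug Safety, treatment is stopped for symptoms of hypervitaminosis D or hypercalcemia, and the vitamin D, calcium and albumin checks follow supplementation. Group B's vitamin D and albumin are measured at week 24. None of this prevents dosing a pregnant woman.

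6. **Whether conception can be discounted.** Entry needs any two of three features, so chronic anovulation is not required. The cover letter lists irregular cycles as a feature of PCOS, so a missed period is a weak signal here. The available text requires no contraception during the study.

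7. **Number of unchecked steps.** With 71 women per group and before any loss to follow-up:
   - Group B injections at or after week 12: up to 71
   - Group A starts of Glucophage and Progeffik at week 12: up to 71
   - Treatment changes with no named pregnancy check: 71 + 71 = 142

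These count treatment changes, not expected pregnancies. The documents give no conception rate, and none is assumed.

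**The case against.** The strongest reply is that this argues from silence. The protocol states the right rule and names no method for establishing several other exclusions either, such as tuberculosis or Cushing's syndrome. Gynecologists and endocrinologists are among the co-investigators, a consultation precedes the switch, and research staff keep in contact with participants. The available text also lacks the consent pages, some earlier material and Figure 6, where pregnancy or contraception might be mentioned.

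Part of this stands. The consultation may catch some cases, and the finding is limited to the text available. But the week-12 tests are given as a specific list in a complete sentence, and the delayed start itself creates the interval. A pre-dose safety check also belongs in the protocol; it is not something usually left to an analysis plan.

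Three stronger readings are tempting, and the documents do not support them.

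- **Group A's week-0 injection has the same gap.** A reader might infer this from Data Collection: "Randomization and drug dispensing will be followed by detailed history, physical examination, biophysical and biochemical parameters estimation by research team". But eligibility, including the vitamin D, calcium, ALT and creatinine limits, is settled before invitation and randomization, and that sentence reads most naturally as describing the capture of study data. An unnamed test at entry is only missing detail.
- **The trial leaves women without contraception.** The drug exclusions include "oral contraceptives, hormonal replacement therapy, glucocorticoids, calcium supplementation", but the list concerns use before the study. It does not prohibit oral contraceptives during the study and bars no other method.
- **Harm or event numbers can be stated.** No part of the protocol says that these drugs harm a pregnancy, and no event rate can be derived. The point rests on the trial's own exclusion and on the irreversibility of the dose.

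**Conclusion.** The concern holds for the week-12 visit. Followed exactly as written, the protocol can give Group B's injection, or start Group A's second-period drugs, in a woman who conceived after entry and whom its own criterion excludes. Group B is the more serious case because the dose cannot be withdrawn.

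The extent is up to 71 injections and 71 drug starts at or after a step with no named pregnancy check. The number of pregnancies affected is unknown. The conclusion assumes that the material not available contains no such check. It implies no bias in the treatment comparison and no error in the sample size. It is a cheap improvement that should be made.

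**What to change.** In Table 2 and in the description of the 12-week visit, require a negative pregnancy test in both groups before any treatment change. A urine test would do, or hCG on the blood already being drawn, provided the result is back before the injection is given or the new drugs are dispensed.

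If the test is positive:

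- withhold the injection in Group B, or Glucophage and Progeffik in Group A;
- have the consultant review all study drugs, including the standard treatment that Group B already takes and the calcium in Group A;
- keep the woman in the intention-to-treat analysis in her randomized group;
- report the number of such cases by group alongside the week-24 results, since outcomes measured during pregnancy may need separate interpretation.

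The cost is one inexpensive test at an existing visit. A few women may not receive their second-period treatment. The planned sample size need not change.
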